The CP288 Coloplast investigational products are non-CE marked stoma products based on the [REDACTED] and a [REDACTED] products to which comprises of a [REDACTED]. The comparator products are considered Standard of Care or products considered to be part of Standard of Care in coming years, and include:

1-piece

2-piece

They are considered the newest products launched by the largest manufacturers covering the majority of the market.

Intended purpose

The product is intended to support collection of output from a stoma and to provide a [REDACTED] between peristomal skin and stoma output.

Aim and objective(s)

The **aim** of this investigation is to investigate the performance and safety of a new baseplate [REDACTED] which is expected to reduce peristomal skin complications induced by output.

The **primary objective** is to investigate whether a new baseplate with a [REDACTED]

The **secondary objective** is to evaluate the [REDACTED] for the peristomal skin condition.

Design of the investigation

This investigation is a randomised, controlled, open-label, comparative, cross-over, multicentre investigation, with two test periods. In total, 96 subjects will be included and randomised, and each subject will have three test visits overseen by the Principal Investigator, or delegate. Each subject will be enrolled for $2 \times 42^{\pm 3}$ days in total for the entire investigation, thus for a maximum of 90 days. The subjects will test the non-CE marked Investigational product and one of the five comparator investigational products in randomised order.

Expected duration of the clinical investigation:

The investigation will be conducted in January 2020 through May 2020.

Primary endpoint

- Max itching score within a week at steady state

For Secondary and explorative endpoints please see Appendix 1 - Endpoints.

.

CONFIDENTIAL

Population/subjects

Subjects with an ileostomy or colostomy with liquid output, currently using a flat (e.g. non-convex/concave) baseplate.

To take a potential drop-out (20%) into account it is recommended to include a total of 48 1-piece and 48 2-piece users, resulting in a total of 96 subjects included and randomised.

The subjects will be included by competitive recruitment in up to 15 sites in five different countries (UK, Germany, the Netherlands, Italy and Norway).

Investigation approval

1.1. Principal Investigators

This clinical investigation involves up to 15 sites in five different countries; United Kingdom, Germany, Italy, The Netherlands and Norway.

The Clinical Manager is responsible for maintaining an updated list of all PIs, investigational sites and institutions in the Sponsor File.

Qualified site personnel can perform investigational related tasks per the Principal Investigator's (PI) delegation. This delegation must be documented in the 'Site Personal Signature and Delegation List' for each site. All PIs and delegates will receive training in all aspects of the investigation and before they can begin any

CONFIDENTIAL

investigational related tasks. The training must be documented in the 'Clinical Investigation Training Log' at each site. The PI is responsible for maintaining these logs.

1.2. Other vendors

Clinical Research Organizations (CROs) may be used to help conduct the investigation as Sponsor representatives in one or more countries. The CROs, their role and responsibilities will be listed in the 'Site Personnel and Contact Details List'.

The company [REDACTED] will help with the validation of the [REDACTED]
[REDACTED]

2. Rational and justification for conduct of the clinical investigation

People with intestinal stomas (especially ileostomists) have, despite development of better stoma products, problems with leakage induced peristomal skin complications which influence quality of life negatively¹². To overcome this, Coloplast A/S has developed a [REDACTED]. The aim is to evaluate of whether the new baseplate can reduce peristomal skin complication induced by output.

3. Aim and Objective(s) for the clinical investigation

The **aim** of this investigation is to investigate the performance and safety of a new baseplate [REDACTED]
[REDACTED] which is expected to reduce peristomal skin complications induced by output.

The **primary objective** is to investigate whether a new baseplate [REDACTED] can reduce peristomal skin complications induced by output.

[figure not shown]
The **secondary objective** is to evaluate the [REDACTED] for the peristomal skin condition.

¹ Porret T et al. DialogueStudy: An international real-life study of stoma care nursing using a new ostomy appliance. *Gastrointestinal Nursing*. 2011 Mar 9(2) (Supplement): 1-24.

² 5] Nybaek H, Knudsen DB, Laursen TN, Karlsmark T, and Jernec GB. Quality of life assessment among patients with peristomal skin disease. *Eur J Gastroenterol Hepatol*. 2010 Feb; 22(2): 139-43

CONFIDENTIAL

4. Design of the clinical investigation

4.1. General

This investigation is a randomised, controlled, open-label, comparative, cross-over, multicentre investigation, with two test periods. In total 96 subjects will be included and randomised, and each subject will have three test visits overseen by the Principal Investigator, or delegate. Each subject will be enrolled for $2 \times 42 \pm 3$ days in total for the entire investigation, thus for a maximum of 90 days. The subjects will test the Coloplast investigational product and one of the comparator products in randomised order.

Before the test periods, the subjects are invited for an information and inclusion visit (V0). Subjects sign all consent forms at the visit before continuing the investigation. During their participation the subjects will complete three test visits (V1, V2 and V3). The visits can be at the Principal Investigators clinic or in the subject's home depending of the nature of the site. In addition, the Principal Investigator, or delegate, will call the subjects every second week during the test periods, thus four phone calls during the investigation.

During the test visits both the subject and the Principal Investigator, or delegate, will complete questionnaires about the subjects peristomal skin condition, the stoma, use and handling of the products, leakage, quality of life and preference, and discuss/record any adverse events.

At every product (1pc) or baseplate (2pc) change the subjects will be asked to take photos of their stoma and peristomal skin and the backside (adhesive side) of the used product with a Clinical Trial App in a smartphone.

Coloplast will provide both the test product and the comparator product for all subjects via the Principal Investigator, based on the subject's usual changing pattern.

If a subject experiences problem with one of the investigational products during the investigation, he/she should contact the investigator for advice. The investigator may reschedule the next visit, e.g. to move it forward to resolve the issue or to monitor an AE. Subjects that can/will not complete a test period with a test product may move forward to the next visit and test period instead of dropping out of the investigation. In this case, the subject may use his/her own product until the next visit. However, this must be documented by the Principal Investigator. The next visits should be scheduled as soon as possible.

CONFIDENTIAL

Please see section 7(Procedures) for more information about procedures during the investigation.

4.2. Total expected duration of the clinical investigation

The dates below are approximate, and no subjects will be enrolled before all required approvals have been obtained.

- First subject enrolled (January - 2020).
- Last subject enrolled (February - 2020).
- Last subject completed (May - 2020).
- Final report (November - 2020).

4.3. Discussion of clinical investigation design

The open-label, randomised, controlled, comparative, cross-over design was selected for CP288 based on the following advantages:

Randomised:

- The randomisation ensures that the study effect, including selection bias and confounding covariates are adjusted for.

Cross-over:

- The influence of confounding covariates is reduced because each cross-over subject serve as his or her own control.
- Cross over design allows us to assess user preference as all users will try both the new non-CE marked product and one of five CE marked products
- Subjects are their own control and fewer subjects need to be included, even though the test period is longer.
- Requires fewer subjects than parallel designs.

Open label:

- The investigation is not blinded because the Coloplast investigational product and comparators are visibly different from each other.

Enrolment period:

- The duration of the test periods ($42^{\pm 3}$ days) and number of visits should be adequate to assess data on the wear time, leakage pattern, and skin condition of the subjects. The investigational products are tested for $42^{\pm 3}$ days to ensure that the skin will have time to adjust to new conditions, reach a steady state, and for the subjects to test an adequate number of products to give a thorough evaluation of the products.

To account for a possible carry-over effect the steady state period of the treatment period begins after three weeks of product use as it is anticipated that the skin has adapted to the new product after three weeks. The statistical analysis will evaluate if there are signs of a carry-over effect and take that into consideration when presenting the results.

CONFIDENTIAL

4.4. Endpoints

Primary, secondary and explorative endpoints are mentioned on a high level. Endpoint details and flow-chart of measures are presented in Appendix 1 - Endpoints, Appendix 2 – Leakage scale questionnaire and Appendix 3 - Quality of life questionnaire.

4.4.1. Primary endpoint

- Maximum itching score within one week at steady state

4.4.2. Secondary, explorative and safety endpoints

Mentioned by group name.

Secondary endpoints	Explorative endpoints	Safety endpoints

- Itching- Pain- Burning- Bleeding/ Weeping or moist skin/Ulcers or sores- Overall physical discomfort- Overall ability to move around- Overall ability to stick the stoma bag adhesive to your skin- Discoloration- Intensity- [REDACTED]- [REDACTED]	
- Stoma behaviour- Feeling of security- Handling- Leakage- Quality of life- Preference- Reason for change- Use of accessories- Ballooning	
- Adverse events- Device deficiencies

4.4.3. Rationale for the selection of endpoints

The skin endpoints are subjective and objective parameters describing the health of the peristomal skin. Therefore, these are essential to investigate if the new baseplate [REDACTED] can reduce peristomal skin complications induced by output.

[REDACTED] the baseplate and the possible effect [REDACTED] could affect feeling of security, leakage, handling, wear time and quality of life and are reasons why associated exploratory endpoints are assessed in this investigation.

Adverse events and device deficiencies comprise safety parameters.

4.4.4. Baseline data

Baseline data are mentioned on a high level. Endpoint details and flow-chart of measures are presented in Appendix 4 – Baseline data. The data are registered at the first test visit (V1) by Principal Investigator, or a delegate.

- Inclusion and randomisation data
- Demographics
- Stoma information
- Current product usage
- Changing routine
- Peristomal skin area
- Assessment of body profile
- Frequency of skin complications
- Treatment of skin complications
- Leakage

CONFIDENTIAL

4.5. Randomisation Procedure

All subjects that meet the inclusion and exclusion criteria will be randomised to one of two treatment arms. Each arm examines the non-CE marked investigational product and one of the CE marked comparator investigational products in the following order:

- Arm A: The non-CE marked investigational product, then one of the five CE marked comparators investigational products.
- Arm B: One of the five CE marked comparators investigational products, then the non-CE marked investigational product.

There will be one randomisation list for the subjects normally using a 1-piece product and one for subjects normally using a 2-piece product. This is to stratify the two types of subjects to the treatment arms. The randomisations list will consist of blocks of ten, and centralised.

4.6. Blinding

No blinding will be used in this investigation, as it is not possible to blind the products due to visible differences.

CONFIDENTIAL

5. Investigational products

5.1. The non-CE marked Investigational product

5.1.1. Description of the non-CE marked investigational product

A series of horizontal black bars of varying lengths, suggesting a visual representation of data or a technical diagram. The bars are arranged in a grid-like pattern, with some bars being significantly longer than others, creating a sense of depth or magnitude.

Table 1: Overview of product specifications for the non-CE marked investigational product

5.1.2. Manufacturing

Coloplast A/S, [name], manufactures the non-CE marked Investigational Product.

5.1.3. Intended purpose of the investigational product in the clinical investigation

The non-CE marked investigational product is intended to support collection of output from a stoma and to provide a [REDACTED] between peristomal skin and stomal output.

5.1.4. Intended population for the investigational products

The product is indicated for use with surgically created ileostomies and colostomies with liquid output. The product is indicated for adults.

CONFIDENTIAL

5.1.5. Instruction for use

The handling of the non-CE marked investigational product is described in detail in the Instruction for Use (IFU), which is included in all boxes with the products. It is stated in the IFU that the investigational products are for single-use and must be stored horizontally under dry and not freezing conditions and should be kept away from direct sunlight. Reprocessing, washing, disinfection, and sterilisation may compromise product characteristics, causing additional risk of physical harm to or infection of the user.

All Principal Investigators, and delegates will receive training by the sponsor and/or principal investigator in the handling and correct use of the investigational products. The Principal Investigator, or delegate, will train the subjects in the correct use of the test products.

5.1.6. Total number of investigational products intended for the clinical investigation

The subjects will be included for 42^{±3} days per test period, for a total of up to 90 days.

Subjects using 1-piece products are expected to change their products every day. Therefore, they are expected to use 45 test products and 45 comparator products during their participation.

Two-piece users are expected to use two baseplates every three days. Therefore, they are expected to use 30 test product baseplates and 30 comparator baseplates during their participation.

5.2. Comparator investigational product(s)

The following comparator products has been chosen for this investigation:

1P:

A series of five horizontal black redaction bars of varying lengths, representing a list of 1P comparator products.

2P:

A series of five horizontal black redaction bars of varying lengths, representing a list of 2P comparator products.

The comparator investigational products are considered Standard of Care or products considered to be part of Standard of Care in coming years, and therefore the newest products launched by biggest manufacturers covering the majority of the market.

The comparator products are already on the market and will be used within the intended purpose in this clinical investigation.

CONFIDENTIAL

6. Clinical Investigation population

Based on the sample size calculation (see section 11.2) 48 1-piece and 48 2-piece users should be included and randomised.

The subjects will be included by competitive recruitment in up to 15 sites in five different countries (UK, Germany, the Netherlands, Italy and Norway).

6.1. Eligibility criteria

To be included in the investigation, the subjects must comply with the selection criteria described below

6.1.1. Inclusion criteria

Inclusion criteria	To be included in the investigation a subject must comply with the following inclusion criteria:	Justification for inclusion criteria
1.	Has given written consent to participate by signing the Informed Consent Signature Form	To ensure that the subject has been given written and oral information regarding the investigation, and know enough about the investigation to decide participation
2.	Has an ileostomy or colostomy with liquid output* *Definition of liquid output: Six-Seven in the Bristol scale (Appendix 5 - Bristol scale)	The product is indicated for use with surgically ileostomies and colostomies with liquid output.
3.	Currently using a flat product	The test product is a flat (i.e. non-convex or non-concave) product
4.	Be at least 18 years of age and have full legal capacity	To meet the Helsinki Declaration
5.	Have had their stoma for at least three months (90 days)	To ensure that the initial post-operative problems are overcome, and that the subject are used to having a stoma as well as changing the product before entering the investigation
6.	Can use a product with a max cut size of 40 mm	The cut max of one comparator is 40 mm.
7.	Has experienced leakage* under the baseplate at least three times within the last fourteen days. *Leakage defined as output seeping under the baseplate (Appendix 6 – Classification of leakage)	To ensure that the user has potential leakage induced skin complications
8.	Has symptoms of peristomal skin complications or has peristomal skin complications defined by at least one of the below a) Has experienced symptoms of skin complications (itching, burning, pain) within the last fourteen days b) Has experienced red skin in the inner circle (within three cm from stoma edge) within the last fourteen days c) Has skin complication (assessed by Principal Investigator, or delegate) in the inner circle (within three cm from stoma edge) of the peristomal area	To ensure that the user has skin complications in the peristomal area.
9.	Is able to handle the electronic diary (questionnaire/photo) themselves	To answer the CRF questions and take photo the subjects must be able to handle the electronic diary themselves.

CONFIDENTIAL

Inclusion criteria		Justification for inclusion criteria
To be included in the investigation a subject must comply with the following inclusion criteria:		
10. Is able to handle (apply, remove, cut etc.) the product themselves		The subjects must be able to handle the product/baseplate themselves to evaluate the handling of the product, which is an endpoint in this investigation.
11. Is willing to not use barrier film or barrier cream during the investigation		The use of barrier film or cream could compromise the effect of the new baseplate
12. Is willing and suitable (determined by Principal Investigator, or delegate) to use a flat custom cut one-piece open or a two-piece open product during the investigation.		To ensure compliance with the protocol during the investigation
13. Is willing to change the product (1pc) or baseplate (2pc) at least every fourth days.		To ensure enough changes is recorded in the CRF

6.1.2. Exclusion criteria

Exclusion criteria		Justification for exclusion criteria:
A subject is not allowed to participate in case he/she:		
1. Is currently receiving or have within the past 60 days received radio-and/or chemotherapy	
 - low doses chemotherapy (assessed by Principal Investigator) is allowed for indications other than cancer 	The skin undergoes major changes because of radio-and/or chemotherapy, and therefore, the skin might be more fragile to product changes.
2. Is currently receiving or have within the past month received topical steroid treatment in the peristomal skin area, e.g. lotion or spray.	
 - Low dose systemic steroid treatment (e.g. inhalation) assessed by the Principal Investigator are allowed. - Other systemic steroid treatment (e.g. injection, or tablet) are not allowed. 	Steroid product on peristomal skin may interfere with the skin condition. Use of steroid product can make the skin more fragile to baseplate change.
3. Is breastfeeding		Even though the ingredients and the recipes have been approved for humans, their effect on embryos, foetuses, and infants are unknown.
4. Is pregnant (based on pregnancy test - urine)		Even though the ingredients and the recipes have been approved for humans, their effect on embryos, foetuses, and infants are unknown.
5. Has known hypersensitivity towards any of the products used in the investigation		It is not ethical to include persons that know they are allergic to the products used in the investigation and it would also create bias, as these persons would give the product they are allergic to a more negative rating and most likely also create an AE.

CONFIDENTIAL

6.1.3. Pregnancy and breastfeeding

For female subjects with childbearing potential (they have had at least one period during the last 12 months), a urine pregnancy test will be performed at the inclusion visit (V0) after signed informed consent, to ensure the subject is not pregnant. The urine pregnancy test will be performed by dipstick at the investigation site. Furthermore, the female subjects should not be breastfeeding, when participating in the clinical investigation.

Principal Investigator must talk to the women about the risk of and how to avoid unwanted pregnancy at inclusion and at every test period the subject participates in hereafter.

If the subject is sexually active, she should be willing to practice appropriate contraceptive methods until the end of the investigation.

Appropriate contraceptive methods are:

- sexual abstinence (in some cases when the women are older than 50 years, but are not yet post-menopausal, the Principal Investigator may evaluate that it is not reasonable to ask these women to start using safe contraceptives for the duration of the investigation)
- oral contraceptives
- trans dermal patches
- depot injection of a progestogen drug
- double barrier method
- condom or occlusive cap (diaphragm or cervical/vault caps) plus spermicidal agent
- intrauterine device (IUD)
- intrauterine system (IUS)
- implant, or vaginal ring (placed at least 4 weeks before the first test period)
- male partner sterilisation before the female participant's entry into the investigation and is the sole sexual partner for that female participant.

However, national requirements should always be followed.

If the subject becomes pregnant during the investigation, it is important, that the subject informs the Principal Investigator, or delegate, immediately. Hereafter the subject will be withdrawn from the investigation.

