6.3.1. Screening failures

Screening failures are considered subjects that have signed the informed consent form and been included based on in- and exclusion criteria, but not yet randomised.

Subjects that have signed the informed consent form but fails to comply with the in- and exclusion criteria are also considered screening failures.

Screening failures can be replaced by a new subject.

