7.1.1. Site visits

Visit 0 (Inclusion visit)

If a potential subject is interested in participating after the first contact, a visit (visit 0) will be arranged in a room reserved to ensure privacy and quiet surroundings at the investigators clinic/department. When arranging the visit, it will be ensured, that the subject has received the Subject Information Form prior to the visit. The subjects will receive both written and verbal information to ensure that the subject understands what was read and explained and can freely agree to participate in the investigation. The subject will, beforehand, also be informed about the possibility of bringing a companion to Visit 0 and to any possible subsequent visits. During the visit the principal Investigator, or delegate, will provide oral information about the investigation based on the Subject Information Form. The subject has the right to wait before deciding on participation.

If/when subjects decide to participate, they will be asked to sign the Informed Consent Signature Form. Hereafter, relevant female subjects will be asked to give a urine sample for a pregnancy test. The sample will be destroyed right after the test. If a subject so desires, and it is certain that it is understood what the investigation entails, and the relevant form has been signed the subjects are considered enrolled in the investigation. Enrolled subjects that are deemed eligible per the inclusion/exclusion criteria are allocated a subject number.

Visit 0 and visit 1 can be combined.

Test visits (V1, V2 and V3)

During test visit 1, the subject will be randomised to either treatment Arm A or Arm B and will be allocated a randomisation number. Hereafter the baseline questions will be completed by the Principal Investigator, or delegate. The subjects will be introduced to the clinical trial app and how to complete the questionnaires and take photos.

At test visit 1 and 2 investigational products (CE marked comparator products or non-CE marked Investigational Product) will be handed out according to the randomisation. The subject will only be informed about which product to wear in the upcoming period. At the visits the subjects will be trained according to the IFU, in preparation of the product (e.g. hole size), preparation of skin before application (e.g. cleaning and wiping), application of the product (e.g. correct position and applying pressure to the baseplate), removal of product and storage of the product.

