7.2. Flow-chart

Table 3 chart showing the connection between visits and assessments. ¹ Investigator, or delegated personnel.

Assessment	Performed by	Visit 3		
		Inclusion visit (V0)	Test visit (V1)	Test visit (V2)
Oral information	Investigator ¹	X		
Written informed consent	Subject	X		
Check of inclusion and exclusion criteria	Investigator ¹	X		
Pregnancy test (urine sample) – females only	Subject	X		
Subject number allocated	Investigator	X		
Randomisation	Investigator	X		
Registration of Baseline data	Investigator ¹	X		
Introduction to Clinical Trial App	Investigator ¹	X	X	X
Assessment of subject wellbeing and compliance with CIP	Subject		X	X
Record change of product in Clinical Trial App, including photos and completion of questions related to change of product	Investigator		X	X
Photo of peristomal skin for assessment of changes in skin condition	Investigator		X	X
Complete visit questions in eCRF	Investigator ¹		X	X
Complete visit questions in Clinical Trial App	Subject		X	X
Investigational product hand-out according to randomisation	Investigator ¹		X	X
Subjects trained in how to prepare skin for the investigational product handed out, and how to use, handle, cut and store the product, according to IFU.	Investigator ¹		X	X
Hand-out remuneration and obtain signature	Investigator ¹ /subject		X	X
Arrange dates for the next test visit and calls	Investigation ¹		X	X
Inform Clinical Manager about scheduled visits	Investigation ¹		X	X
Adverse events incl. supplementary information	Investigation ¹		X	X
Device Deficiencies	Investigation ¹		X	X
Concomitant medication	Investigation ¹	X	X	X

CONFIDENTIAL

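### The entry pregnancy test in section 6.1.3 is tied to having had a period in the past year, so a fertile woman without periods need not be tested

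*Combined protocol and SAP*

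**What the plan says.** Exclusion criterion 4 in section 6.1.2 bars a subject who "Is pregnant (based on pregnancy test - urine" test). The reason given beside it is: "Even though the ingredients and the recipes have been approved for humans, their effect on embryos, foetuses, and infants are unknown".

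Section 6.1.3 says who takes the test at V0: "female subjects with childbearing potential (they have had at least one period during the last 12 months), a urine pregnancy test". The same section lists accepted contraceptive methods, among them "depot injection of a progestogen drug", an intrauterine system and an implant. It closes the list with "However, national requirements should always be followed".

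Two other places mention the test. Section 7.1.1, under Visit 0, says: "Hereafter, relevant female subjects will be asked to give a urine sample for a pregnancy test". The flow-chart in section 7.2 has a row labelled "Pregnancy test (urine sample) – females only". Neither defines who must be tested.

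**The concern.** A missing period over the past year is used as the sole marker that a woman cannot conceive. That works for menopause, but periods can be absent for a year in a woman who is still fertile. Illness can cause this, and so can some of the hormonal methods that section 6.1.3 itself accepts. That these causes can stop periods is general clinical knowledge, not something the documents state. The gap in the definition does not depend on any one cause.

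What is at stake is the protection of an individual subject. Criterion 4 rests on a test result, and for this woman the plan does not require one. V0 is the only visit at which a test is scheduled. Section 7.1.1 allows V0 and V1 to be combined, so she could receive product the same day.

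**Working it through.** No figure in the plan bears on this point, so the check is to apply the rule in section 6.1.3 to each kind of female subject and compare the result with the reason given for criterion 4.

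1. *Regular periods.* Inside the bracket, so tested. Consistent with the reason.
2. *Already pregnant, with normal periods before that.* A pregnancy is shorter than 12 months, so her last period lies inside the window and she is tested. The rule works here.
3. *Post-menopausal for more than a year.* Outside the bracket, not tested. Consistent with the reason.
4. *Permanently sterile and without periods.* Outside the bracket, not tested. Consistent with the reason.
5. *Neither sterile nor post-menopausal, but no period for over 12 months from another cause.* Outside the bracket, so no test is required. The reason for criterion 4 applies to her, so the rule gives the wrong answer.

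Next, whether any other text requires a test in case 5:

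- *Criterion 4 (section 6.1.2)* bars any pregnant subject and names the urine test as the basis, but does not say who must take it.
- *Section 7.1.1* speaks of relevant female subjects. The natural reading refers back to section 6.1.3 and so carries the same gap.
- *The flow-chart (section 7.2)* labels the row for females. This most likely means only that the row does not apply to men.
- *The national-requirements sentence (section 6.1.3)* states no testing rule. Section 16 places national regulations in country-specific plans, which are not among the documents.

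None of the four requires the test. Section 6.1.3 already uses the idea of a woman who is not yet post-menopausal when it discusses abstinence after age 50. The concept needed is therefore in the plan, but the testing rule does not use it.

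The longest exposure if a pregnancy were missed at V0 and not reported follows from the period length in section 4.1: 42 + 3 = 45 days on the non-CE marked product, within at most 2 × 45 = 90 days of test periods.

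**The case against.** The strongest case against the point has four parts.

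- *Not required is not the same as not allowed.* Criterion 4 has no childbearing limit and is checked for every subject, so an investigator in doubt already has grounds to test. This stands and lowers the risk, but it leaves the test to discretion.
- *The group is very narrow.* Women using an accepted hormonal method are unlikely to be pregnant, and breastfeeding women, who may also lack periods, are excluded separately by criterion 3. This also stands.
- *There are other safeguards.* Sections 6.1.3, 7.1.2 and 7.1.4 provide counselling on pregnancy at inclusion and in each test period, contraception for sexually active women, phone calls and safety assessment at every contact. These are real, but they rely on the woman knowing of and reporting a pregnancy. They do not replace a test.
- *National rules may close the gap.* They may in some of the five countries, but this cannot be checked from the documents.

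A reader might also infer that the three descriptions of the test conflict, so that sites would handle the same woman differently. The documents do not support that. Only section 6.1.3 sets a rule, section 7.1.1 points back to it, and the flow-chart label is shorthand. Sections 1.1 and 7.1 also require site staff to be trained in the procedures before they start. If the label did mean all women, the woman in question would be tested, which would reduce the harm.

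**Conclusion.** The point holds as a small defect of definition. Section 6.1.3 leaves out fertile women who have had no period for a year, and nothing else in the plan requires them to be tested, although the plan's own reason for excluding pregnancy covers them.

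Its size is probably very small. The documents give no figure from which to derive the number affected, and none is assumed here. Missed pregnancies would be fewer still. A reader might infer that pregnant women are likely to enter the trial or that the results are at risk, but neither follows. The efficacy analysis is not affected.

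The conclusion rests on reading the bracket literally as the definition, and on the country-specific plans not already setting a wider rule. It is worth correcting because the correction is cheap, but it does not justify an amendment of its own.

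**What to change.** In section 6.1.3, replace the bracket so that childbearing potential means *every female subject who is neither permanently sterile nor post-menopausal (at least 12 months without a period and no other medical or contraceptive cause)*, and test all such women at V0. Sections 7.1.1 and 7.2 need no rule of their own and may simply refer to section 6.1.3. National requirements continue to apply. No new data field is needed, because Appendix 4 already records the check of the exclusion criteria.

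The cost is one dipstick for each additional woman, at a visit already scheduled. The number is unknown but should be a few. A positive test before randomisation makes her a screening failure, and "Screening failures can be replaced by a new subject", so the planned 96 randomised subjects are not reduced.

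Under section 13 the change needs a signed amendment and notification to the ethics committee, and to the competent authority where appropriate. It is best combined with another amendment.
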